**NCT# 04552132**

**May 2, 2022**

## Pain Assessment Protocol

This study protocol was approved by the Institutional Review Board of Saint Louis University, Saint Louis, MO (Protocol Number 31359). Patients were recruited for this study from the patients seen at the Center for Advanced Dental Education at Saint Louis University from September 2020 through March 2022. Informed consent was obtained from each patient for participation in this study. The following inclusion criteria were utilized for participation in the study: adults fully able to provide informed consent, with restorable, symptomatic molar teeth (reporting  $\geq 20$ mm on the VAS during the previous 24 hours) seeking endodontic therapy. Patients where both Ibuprofen and Acetaminophen were contraindicated, patients with chronic pain issues for which they regularly need to consume analgesics, and patients having taken analgesics or antibiotics within the previous 6 hours were excluded from this study.

The first patient treated in the study was randomized by coin toss, followed by an alternating pattern thereafter for the 2 groups: GentleWave (GWS) (n=16) or EndoActivator (EA) (n=17). Prior to their clinical evaluation, the patients marked on: 1) a 100mm VAS instrument where they felt best represented their degree of pain experienced at that moment, and 2) a 2nd 100mm VAS instrument their maximum level of pain during the previous 24 hours. Clinical evaluation of the patient included percussion and palpation testing, periodontal probing measurements, thermal pulp sensibility testing using a cold source (Endo Ice), and an evaluation of tooth mobility. Radiographic examination (XDR Radiology, Los Angeles, CA) included bitewing, straight-on periapical, angled periapical, and 4X4 cm high-resolution limited field of view cone beam computed tomography (CBCT) (CAREstream 9600-CAREstream Dental, Atlanta, GA) imaging.

Following the administration of topical anesthetic (20% Benzocaine), the same high-level of anesthetic was administered to all patients, in order to standardize the number of injections received by the participants. If supplemental anesthesia was required, intrapulpal injections were performed for vital teeth and periodontal ligament injections were performed for necrotic teeth.

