#### CBCT Healing Assessment and statistical analysis

Patients (GWS=12, EA=14), were recalled at 12 months postoperative, and the same imaging and clinical endodontic testing was done as had been performed preoperatively. A 3-D volumetric analysis using ITK Snap software (ITK SNAP, Philadelphia, PA) was completed

to measure the volume of pre-and-post-operative periapical findings in mm^3. Each individual root was then assigned a 3Droot classification of either healed (normal PDL around the root at recall), healing (reduced size of finding), or diseased (same or larger size finding). Pearson's Chi squared test was used to evaluate if there was any difference in 3Droot healing outcomes between the GWS and EA groups. Results were considered significant if the p≤.05.

Clinical tooth healing classification based on clinical examination and patient report (Ctooth)

Teeth were classified as being clinically successful if the patient had no symptoms other than mild tenderness to percussion. Teeth were not considered as failures due to mild percussion sensitivity alone, as long as the patient reported no pain when chewing.

Pearson's Chi squared test was used to evaluate if there was any difference in Ctooth healing outcomes between the GWS and EA groups. Results were considered significant if the p≤.05.

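### The 12-month healing comparisons yield only a significance verdict from 12 v 14 patients; a difference with a 95% confidence interval is needed, because p>.05 cannot support a conclusion of no difference

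*Combined protocol and SAP*

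**What the plan says.** The section on CBCT healing assessment opens with the numbers available: "Patients (GWS=12, EA=14), were recalled at 12 months postoperative". The Pain Assessment Protocol gives the treated numbers as "GentleWave (GWS) (n=16) or EndoActivator (EA) (n=17", so 26 of 33 patients contribute at 12 months.

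Two outcomes are then defined:

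- **3Droot** is scored per root: "Each individual root was then assigned a 3Droot classification of either healed", with healing and diseased as the other two categories. The number of roots is not given.
- **Ctooth** is a yes/no outcome per tooth: "Teeth were classified as being clinically successful if the patient had no symptoms other than mild tenderness to percussion".

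Each outcome gets one test. For the roots, "Pearson's Chi squared test was used to evaluate if there was any difference in 3Droot healing outcomes between the GWS and EA groups"; for the teeth, "Pearson's Chi squared test was used to evaluate if there was any difference in Ctooth healing outcomes between the GWS and EA groups". The decision rule for both is "Results were considered significant if the p≤.05". The document plans no effect estimate, confidence interval, margin or power for either outcome, and does not say how a non-significant result will be worded.

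**The concern.** The question asked is whether the arms differ in healing, and the only answer provided for is significant or not significant. With 12 and 14 patients, a non-significant answer fits both equal healing and a large deficit in either arm, and a p-value alone does not tell the reader which differences remain plausible. Changing the test would not help: an exact or cluster-adjusted p-value also carries no effect size and no precision. At stake is what may be concluded about GentleWave relative to EndoActivator at one year.

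**Working it through.** The documents state no expected success rate, effect size or power, so there is no figure of theirs to reproduce.

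**Inputs from the documents.** m = 12 (GWS), n = 14 (EA), threshold 0.05. Pearson's test is non-directional, so it is paired with a two-sided 95% interval.

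**Assumptions made here.** One tooth per patient for Ctooth; a 20-point yardstick; the true success rates used for power; two or three roots per tooth and the intraclass correlations (ICC) used for 3Droot.

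**Interval.** Take the Wilson limits (l, u) for each arm. With d = p₁ − p₂ (GWS minus EA), Newcombe's limits are

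- lower = d − √[(p₁ − l₁)² + (u₂ − p₂)²]
- upper = d + √[(u₁ − p₁)² + (p₂ − l₂)²]

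*12/12 v 14/14.* When all succeed, the Wilson lower limit is N/(N + 1.96²).

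- GWS: 12/15.84 = 0.758. EA: 14/17.84 = 0.785. Both upper limits are 1.
- Lower = 0 − (1 − 0.758) = -24.2 points; upper = 0 + (1 − 0.785) = +21.5 points. Miettinen-Nurminen gives -25.0 to +22.2.
- Pearson's statistic cannot be computed here, because the expected number of failures is zero.

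*10/12 v 14/14.* Wilson limits are 0.552 to 0.953 and 0.785 to 1; d = -16.7 points.

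- Lower = -0.167 − (0.833 − 0.552) = -44.8 points.
- Upper = -0.167 + √[(0.953 − 0.833)² + (1 − 0.785)²] = +8.0 points.
- Pearson χ² = 26 × (10×0 − 2×14)² / (12 × 14 × 24 × 2) = 20,384/8,064 = 2.53, p = 0.11.

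*11/12 v 13/14.* d = -1.2 points, interval -28.9 to +24.1, p = 0.91.

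**All possible Ctooth results.** There are 13 × 15 = 195 tables. The two in which Pearson is undefined are counted as non-significant.

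| Property | Tables |
|---|---|
| p>.05 | 101 of 195 |
| Lower limit above -20 points | 77 of 195 |
| The same, among tables with p>.05 | 30 of 101 (28 by Miettinen-Nurminen) |
| Lower limit above -20, with GWS equal to or below EA | 0 |
| 20 points excluded in both directions | 0 of 195 |

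The mirror of the fourth row holds for an EA deficit.

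**Power of the planned test.** Sum Bin(a; 12, p_GWS) × Bin(b; 14, p_EA) over the tables with uncorrected Pearson p≤.05.

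| Assumed true GWS v EA | Power | Missed |
|---|---|---|
| 75% v 90% | 0.21 | 79% |
| 60% v 90% | 0.50 | 50% |
| 65% v 95% | 0.59 | 41% |

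**3Droot.** Suppose every root heals in both arms, with k roots per tooth. Dividing the root counts by the design effect 1 + (k − 1) × ICC gives these Newcombe lower limits, in points:

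| k | Independent roots | ICC 0.5 | ICC 0.8 |
|---|---|---|---|
| 2 (24 v 28 roots) | -13.8 | -19.4 | -22.4 |
| 3 (36 v 42 roots) | -9.6 | -17.6 | -21.7 |

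The Ctooth figures therefore do not carry over. What 3Droot can exclude depends on the unstated root count and on the correlation within patient.

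**The case against.** The plan does not equate p>.05 with equal healing. It claims neither equivalence nor non-inferiority, so a reader who infers such a rule is predicting how the result will be reported. That objection stands; the criticism is only that the one stated output could not support that conclusion.

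A reader might also infer that no result of this size could rule out a 20-point GWS deficit. That is false. Among the non-significant Ctooth tables, 30 do so, for example 12/12 v 13/14 (lower limit -17.8, p=0.35). What cannot happen is exclusion when GWS does no better than EA, or exclusion in both directions at once.

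Nor does the rule make nearly every result non-significant: 94 of the 195 tables are significant, and 9/12 v 14/14 gives p=0.047. Both the yardstick and the interval level matter too. A 90% interval for 12/12 v 14/14 has a lower limit of about -18 points.

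Finally, adding an interval changes no data, test or design. That is true, but it does change what the trial may conclude.

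**Conclusion.** The point holds as a gap in reporting, and closing it is a cheap improvement. Both outcomes are reduced to a significance verdict with no estimate or interval. For Ctooth, with one tooth per patient, even complete success in both arms leaves about -24 to +22 points open, and no possible result confines the difference within ±20 points. Under an assumed 75% v 90%, the planned test misses the difference 79% of the time. The 20-point yardstick and the success rates are assumptions, because the documents give none.

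For 3Droot the missing estimate is the same defect, but its size cannot be given without the number of roots and their correlation within patient.

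**What to change.** In the CBCT healing section:

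- **Ctooth.** Make the main result the difference in success proportion, GWS minus EA, with a Newcombe or Miettinen-Nurminen 95% interval. Keep the p-value as secondary.
- **Wording.** State that a result with p>.05 will be reported as the range of differences the interval allows, and not as equal healing.
- **3Droot.** State the number of roots per arm and name the proportion compared, for example roots healed, since there are three categories. Give the difference with a cluster-adjusted score-type 95% interval that allows for roots within patient. A bootstrap over patients is unsuitable: if all roots heal in both arms, every resample gives a difference of zero and the interval has zero width.

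Ctooth needs only counts already collected and a line of code. 3Droot also needs the root count and the clustering adjustment. In all this is a few sentences of analysis text. The price is a less definite conclusion.
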